**Table 1: Lubricating drop details**

Eye drop		Systane® Complete	
Manufacturer	Alcon		
HC License #:	100469		
Device class:	2		
Active ingredients:	Propylene glycol 0.6%		
Preservative:	POLYQUAD 0.001%		

#### 4.3.4 ORDERING CONSUMABLES

---

Study products will be obtained through commercial sources.

#### 4.3.5 DISPOSING OF CONSUMABLES

---

Study products will be disposed of according to UW guidelines.

#### 4.3.6 PRODUCT ACCOUNTABILITY

---

Accountability logs will be kept to include the number bottles received, used, and unused. All products dispensed to participants will be recorded in the study binder.

### 4.4 SCHEDULED AND UNSCHEDULED VISITS

This study has a total of 2 study visits, including the screening visit.

- Visit 1: Screening
- Visit 2: Data collection, including instillation of the study eye drop

#### 4.4.1 STUDY VISITS

---

This study has a total of 2 study visits, including the screening visit. Visit 2 will be scheduled up to 14 days after the screening visit (Visit 1). The total time commitment for the scheduled visits is 4 hours of active participation. The summary of visit codes is shown in Table 2.

**Table 2: Summary of visit codes**

Visit #	Visit code	Study Day	Visits	Duration (hours)
1	V1 (V1-R1 for rescreening)	1	Screening	1.5
2	2	2	Data collection & study exit	2.5

#### 4.4.2 VISIT 1: SCREENING

---

All participants who signed the informed consent letter will be assigned a study ID number. The investigator will determine participant eligibility using the inclusion and exclusion criteria. Ineligible participants will be discontinued from the study. The procedures to be performed are outlined below:

- Participants will attend the screening visit having not used any eye drops or artificial tears on the day of the visit.
- The participant will be required to read and sign an Informed Consent Form prior to enrollment. When the participant has signed the consent form, the participant will be considered to be enrolled in the study.
- Participant demographics and medical history (age, sex, current dry eye treatments, medical conditions, medications, allergies)
- Ocular Surface Disease Index (OSDI) questionnaire
- Monocular and binocular logMAR visual acuity will be recorded with high contrast letters under high illumination with spectacles (if necessary).
- Tear meniscus height (OCULUS Keratograph® 5M)
- Non-invasive Keratograph® break up time (OCULUS Keratograph® 5M)
- The investigator will confirm that the participant meets the eligibility specifications set out in the inclusion criteria to be categorized as either a dry eye or non-dry eye participant. Participants who do not meet this criteria will be discharged and will not continue with the remainder of the screening visit.
- Lipid layer thickness (EASYTEAR®view+)
- Assessment of meibomian gland secretion and expression
- Lid margin assessment
- Slit lamp biomicroscopy
- Meibography (OCULUS Keratograph® 5M)
- Anterior eye photographs of each eye will be taken with a slit lamp camera.
- Participants will practice evaporimetry measurements.
- Measurement of volume within the goggle.
- Slit lamp biomicroscopy (safety check).
- Monocular and binocular logMAR visual acuity will be recorded with high contrast letters under high illumination with spectacles (if necessary).
- The investigator will confirm that the participant meets the eligibility specifications set out in the inclusion and exclusion criteria and is eligible to continue with the study.

#### 4.4.3 VISIT 2: DATA COLLECTION

---

- Participants will attend the visit having been awake for at least 2 hours.
- Participants will not have used any eye drops or artificial tears on the day of the visit.
- Participants will also not have worn any eye makeup on the day of the visit.
- Participants who have used eye drops or artificial tears or have worn eye makeup will be rescheduled.
- Monocular and binocular visual acuity will be recorded with high contrast letters under high illumination with spectacles (if necessary).
- Slit lamp biomicroscopy using white light.
- Participants will be required to adapt to the room environment for at least 15 minutes prior to reporting subjective monocular ratings and performing baseline evaporimetry measurements. The participant will apply thin layer of petroleum jelly will be applied to the skin surrounding the eye using a cotton tipped applicator to minimize the amount of evaporation from the skin.
- The participant will be asked to give subjective monocular ratings for:
  - Comfort
  - Dryness
  - Burning or stinging
- Tear meniscus height (OCULUS Keratograph® 5M)
- Baseline evaporimetry measurements
- Non-invasive Keratograph® break up time (OCULUS Keratograph® 5M)
- Lipid layer thickness (TearScience LipiView® II)
- At least 20 minutes after the initial baseline measurement, the participant will be asked to give subjective monocular ratings for:
  - Comfort
  - Dryness
  - Burning or stinging
- Tear meniscus height (OCULUS Keratograph® 5M)
- Repeated baseline evaporimetry measurements
- Non-invasive Keratograph® break up time (OCULUS Keratograph® 5M)
- Lipid layer thickness (TearScience LipiView® II)
- The participant will wipe away petroleum jelly from the skin surrounding the ocular surface using a tissue.

- One drop of Systane® Complete will be instilled into each eye.
- The participant will apply a thin layer of petroleum jelly to the skin surrounding the eye using a cotton tipped applicator to minimise the amount of evaporation from the skin.
- 10 minutes after instillation of the eye drop, the participant will be asked to give subjective monocular ratings for:
  - Comfort
  - Dryness
  - Burning or stinging
- Tear meniscus height (OCULUS Keratograph® 5M)
- Evaporimetry measurements
- Non-invasive Keratograph® break up time (OCULUS Keratograph® 5M)
- Lipid layer thickness (TearScience LipiView® II)
- 30 minutes after instillation of the eye drop, the participant will be asked to give subjective monocular ratings for:
  - Comfort
  - Dryness
  - Burning or stinging
- Tear meniscus height (OCULUS Keratograph® 5M)
- Evaporimetry measurements
- Non-invasive Keratograph® break up time (OCULUS Keratograph® 5M)
- Lipid layer thickness (TearScience LipiView® II)
- 60 minutes after instillation of the eye drop, the participant will be asked to give subjective monocular ratings for:
  - Comfort
  - Dryness
  - Burning or stinging
- Tear meniscus height (OCULUS Keratograph® 5M)
- Evaporimetry measurements
- Non-invasive Keratograph® break up time (OCULUS Keratograph® 5M)
- Lipid layer thickness (TearScience LipiView® II)
- The participant will wipe away the petroleum from surrounding the ocular surface using a tissue.
- Slit lamp biomicroscopy

- Exit monocular and binocular logMAR visual acuity will be recorded with high contrast letters under high illumination with spectacles (if necessary).

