#### 4.5.16 REMOVAL OF PETROLEUM JELLY

---

To remove petroleum jelly from the skin, the participant will close their eyes and wipe with a tissue in a nasal to temporal direction, with extra care being paid when wiping near the lid margin to avoid contaminating the tear film.

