#### 4.5.17 SUBJECTIVE COMFORT RATINGS

---

Participants will be asked to fill a numerical analog scale for comfort, dryness, and burning or stinging for each eye on a 0-100 scale at the following time points during Visit 2:

- Before eye drop instillation (prior to the first baseline evaporimetry measurement)
- Before eye drop instillation (at least 20 minutes after the initial baseline evaporimetry measurement)
- 10 minutes after eye drop instillation
- 30 minutes after eye drop instillation
- 60 minutes after eye drop instillation

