#### 4.5.18 EVAPORIMETRY

---

The participant will be seated at an adjustable height table and will place their elbows on the table. The participant will hold a pair of modified swimming goggles (Figures 1A and 1B) over their eyes for 20 seconds while their eyes are open. The participant will be prompted to blink every 3 seconds during the measurement using a metronome (<https://www.youtube.com/watch?v=9ypeNJJeKIs>). The goggle will be removed and ventilated in front of a fan until the relative humidity returns to baseline levels. The goggle will then be placed over the eyes for 20 seconds while they are closed to measure the evaporation rate from the skin. Three consecutive measurements of open eye and closed eye measurements will be taken. Recordings of the temperature and relative humidity during the measurement will be saved as a word document and images of the temperature and

humidity versus time plotted as a graph will be saved as a png file. The rate of tear evaporation will be calculated from slope derived from the change in relative humidity over time. The evaporation rate from the ocular surface will be calculated by subtracting the evaporation rate of closed eye from the evaporation rate of the open eye. The average of three ocular surface evaporation rates will be calculated for each eye.

[figure not shown]

Figure 1: (A) Evaporimeter with arrows showing the location of the temperature/humidity sensors in the swimming goggles. (B) View of the front of the evaporimeter.

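### Does wiping off and reapplying petroleum jelly only around the eye drop call for a change to the Visit 2 schedule?

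*Combined protocol and SAP*

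**What the plan says.** Section 4.4.3 gives one sequence for every participant:

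1. The participant waits to "adapt to the room environment for at least 15 minutes" and applies jelly around the eyes.
2. Baseline 1 is taken.
3. Baseline 2 follows on the same layer: "At least 20 minutes after the initial baseline measurement" the ratings are repeated, then the other measurements. Section 4.5.17 gives the same interval for the ratings. No wipe or reapplication is listed between the baselines.
4. "The participant will wipe away petroleum jelly from the skin surrounding the ocular surface using a tissue".
5. One drop is instilled in each eye.
6. "The participant will apply a thin layer of petroleum jelly to the skin surrounding the eye".
7. Readings are taken at 10, 30 and 60 minutes.
8. "The participant will wipe away the petroleum from surrounding the ocular surface using a tissue". No reading follows this last wipe.

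Two other sections bear on the point. Section 4.5.16 has the participant wipe with closed eyes, with "extra care being paid when wiping near the lid margin to avoid contaminating the tear film". Section 4.5.18 takes three open-eye and three closed-eye recordings at each session, and the ocular surface rate is "calculated by subtracting the evaporation rate of closed eye from the evaporation rate of the open eye".

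Sections 4.1.1 to 4.1.3 describe a non-randomized, unmasked pilot. Table 4 tests the effect of the drop for tear evaporation rate only, by repeated-measures ANOVA with Tukey post hocs and a paired t-test. The ratings, tear meniscus height, break-up time and lipid layer thickness enter Table 4 only through correlations with the evaporation rate.

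**The concern.** The first hypothesis in section 3 is that evaporation falls after the drop. With no control arm, the before/after change is the only evidence for it. Every post-drop reading comes after a wipe and a second application, and no pre-drop reading does. If that handling disturbs the tear film, the disturbance is counted as a drop effect. Section 4.5.16 itself treats wiping near the lid margin as a possible contaminant. Baseline 2 looks as if it could serve as a no-drop control for this step, but it is taken before the wipe. More participants would not help, because the sequence is the same for everyone. Section 4.2.1 says the results will inform later sample sizes, so a misattributed change could carry forward.

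The natural suggestion is to add a wipe-and-reapply cycle between the two baselines and to use 10 minutes minus baseline 2 as the comparison that isolates the drop.

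**Working it through.** The plan states no figure on this point. The check asks what each schedule can estimate.

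**Inputs (section 4.4.3).** Five readings: baseline 1 (b1), baseline 2 (b2), and 10, 30 and 60 minutes. Unknowns: level μ, cycle effect c, and drop effects d10, d30 and d60. The cycle indicator is (0,0,1,1,1) on the current schedule and (0,1,1,1,1) with a cycle added before b2.

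**No drift.** There are 5 unknowns. The design matrix has rank 4 on the current schedule, because c appears only as c + d10, c + d30 and c + d60. With the added cycle the rank is 5. This is the apparent gain.

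**Linear drift β per minute.** There are now 6 unknowns. Let b1 be at time 0, b2 at time t2 and the 10 minute reading at time t3.

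- Current schedule:
  - b2 − b1 = βt2, so β is estimable from the undisturbed pair.
  - (10 min) − b1 = βt3 + c + d10, so c + d10 is estimable after removing drift. The same holds at 30 and 60 minutes.
- Added cycle:
  - b2 − b1 = βt2 + c, so drift and cycle cannot be separated.
  - (10 min) − b2 = d10 + β(t3 − t2), so d10 is not estimable without β. The same holds at 30 and 60 minutes.

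The rank is 5 of 6 under both schedules, but what is lost differs. The current schedule confuses only cycle with drop. The altered one leaves drift, cycle and all three drop effects inestimable.

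**Size, as an illustration only.** Assume n = 20, independent readings with unit within-person SD, no true drop effect and no drift. The paired difference then has SD √2 = 1.414. The test is two-sided at 5% with 19 df, and rejection rates come from the noncentral t distribution with noncentrality (net shift/1.414) × √20.

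| Cycle shift (SD) | 10 min − b2, current | Added cycle, same shift | Added cycle, second adds half as much again | Added cycle, effects fully add |
|---|---|---|---|---|
| 0.05 | 5.3% | 5.0% | 5.1% | 5.3% |
| 0.10 | 6.0% | 5.0% | 5.3% | 6.0% |
| 0.25 | 11.7% | 5.0% | 6.6% | 11.7% |
| 0.50 | 32.4% | 5.0% | 11.7% | 32.4% |
| 0.75 | 61.4% | 5.0% | 20.3% | 61.4% |

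Any confounder of these sizes would give the same figures, so they say nothing about jelly in particular.

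**At 30 and 60 minutes.** With the added cycle, the comparison with b2 rejects in 5% if the shift persists. If the shift has gone by 30 minutes, it rejects at the rates in the second column, with the opposite sign. On the current schedule these two cases are reversed. Nothing measured would show which case applies.

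**Precision.** The 95% half-width is 2.093 × SD/√20.

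- 10 min − b2: 2.093 × 1.414/√20 = 0.66 SD, with 32% power for a true 0.5 SD effect.
- 10 min − mean(b1, b2), difference SD √1.5 = 1.225: 2.093 × 1.225/√20 = 0.57 SD, with 41% power.

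Baselines prepared differently could no longer be averaged as like with like, so the first figure would apply.

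**Visit time.** The stated waits are 15 + 20 + 60 = 95 of the 150 minutes in Table 2. This excludes visual acuity, slit lamp and most of the measurement time, so room for another cycle is plausible but not shown.

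**The case for a change.** The strongest case for a change is that the confounding is exact and needs no assumed effect size, and that the route is one the protocol itself recognises. Closed-eye subtraction corrects for skin evaporation. It does not correct for a disturbed tear film in the open eye. One extra cycle is cheap, and if both cycles leave the same lasting shift it brings the 10 minute comparison back to its nominal 5%. The drift argument has limits too: two readings estimate drift imprecisely (b2 − b1 has a half-width of 0.66 SD), and carrying it forward to 60 minutes assumes linearity.

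The confounding stands, and so does the limit on attribution. The remedy is weaker. It gives no gain if the cycles add, and it reverses the bias at two of the three post-drop readings if the effect fades. It also adds another wipe near the lid margin. It gives up the plan's only undisturbed no-drop pair, which is relevant to the validation aim in the Introduction. The documents size neither drift nor a cycle effect, so they give no ground for preferring protection against one over the other.

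That the ratings and other tear-film measures lack a skin correction adds little. They do not measure skin evaporation, and Table 4 plans no before/after test of them.

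Two lesser suggestions remain. Table 4 does not say which pair the paired t-test compares, but this is a detail an analyst can settle sensibly. Tabulating closed-eye rates by time point uses data already collected, but it would leave the tear-film question and every result as they are.

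**Conclusion.** No change to the plan. The before/after change measures the drop together with one wipe and reapplication, time and expectation. An open single-arm design already imposes most of that limit, and an extra cycle would not remove it. Jelly at all five readings, closed-eye subtraction and the wiping precautions narrow the jelly-specific part to a possible tear-film effect of one cycle, of unknown size and direction. Under the working assumptions (n = 20, independent readings), such an effect would hardly matter at 0.1 SD (6.0% rejection against 5%) and would matter at 0.5 SD (32%). The documents give no reason to expect either.

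The added cycle helps only if both cycles leave the same shift and there is no drift, and at 30 and 60 minutes only if that shift also lasts. With linear drift it makes every drop effect inestimable, whereas the current schedule still yields the drift and the drop-plus-cycle effect. The second hypothesis, on baseline differences between dry eye and non-dry eye participants, is unaffected, because both groups have the same jelly handling before the drop.

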### Study Exit

- The study exit form will be completed when a participant exits the study. This will occur either at study completion, or if the participant is discontinued from the study at another time. A study exit form must be completed for all participants who have been given a study number. If in the opinion of the investigator post-study follow-up visits are required, the exit form will be completed after the last follow-up visit.
- The participant will be discharged and will sign the study completion forms and receive remuneration for participating in the study.

### 4.4.4 UNSCHEDULED VISITS

An unscheduled visit is defined as an interim visit requested by the participant or investigator due to an unanticipated problem. Data recorded at these visits will be entered into the database. Only relevant and applicable unscheduled visit information will be included in the final report as deemed necessary by the lead investigator.

## 4.5 STUDY PROCEDURES

Table 3 summarizes the visits and procedures for the study.

**Table 3: Summary of procedures to be conducted at scheduled visits**

Procedure	Visit 1	Visit 2	Instrument/application
Informed consent (screening)	√		Investigator
Demographics	√		Investigator
Medical history	√	√	Investigator
Ocular Surface Disease Index (OSDI)	√		Questionnaire (paper)
VA with spectacles (if necessary)	√	√	Visual acuity chart
Tear meniscus height	√	√	OCULUS Keratograph® 5M
Non-invasive Keratograph® break up time (NIK BUT)	√	√	OCULUS Keratograph® 5M
Lipid layer thickness	√		EASYTEAR®view+
Meibomian gland assessment	√		Meibomian Gland Evaluator (lower lid)

Procedure	Visit 1	Visit 2	Instrument/application
Lid margin assessment	√		Slit lamp
Slit lamp biomicroscopy (with staining)	√	√	Slit lamp
Meibography	√		OCULUS Keratograph® 5M
Anterior eye photography	√		Slit lamp and camera
Evaporimetry practice	√		Prototype evaporimeter
Measurement of volume inside the goggle	√		Modified swimming goggle
Slit lamp biomicroscopy (safety with staining)	√		Slit lamp
Confirmation of inclusion/exclusion criteria	√		Investigator
Slit lamp biomicroscopy (white light)		√	Slit lamp
Subjective assessment (comfort, dryness, burning/stinging)		√	Questionnaire (paper)
Evaporimetry		√	Prototype evaporimeter
Lipid layer thickness		√	TearScience LipiView® II
Application of petroleum jelly		√	Participant
Removal of petroleum jelly		√	Participant
Instillation of eye drop		√	Investigator
Study completion and exit		√	N/A

#### 4.5.1 DEMOGRAPHICS

---

Demographic information will be obtained from the participant, including age and sex.

#### 4.5.2 MEDICAL HISTORY

---

At the screening visit, medical history questions to determine any current medications, current dry eye treatments, allergies and relevant medical conditions will be asked and documented. At subsequent visits, participants will be asked about changes in their medication or medical condition(s).

#### 4.5.3 OCULAR SURFACE DISEASE INDEX (OSDI) QUESTIONNAIRE

---

The OSDI is a dry eye questionnaire that asks the participant to reflect and rate their symptoms of eye dryness in different working conditions and environments over the past week. A higher composite score indicates more severe dryness and scores can range from 0 to 100. A score of <13 will be considered asymptomatic and a score  $\geq 13$  will be symptomatic.

#### 4.5.4 LOGMAR VISUAL ACUITY

---

Distance logMAR visual acuity will be measured using high contrast computer-generated acuity charts in high illumination room lighting. Participants will be asked to read letters, which progressively decrease in size on a computer screen at a viewing distance of 6 meters, with their habitual glasses (if necessary).

#### 4.5.5 TEAR MENISCUS HEIGHT (TMH)

---

The participant will be seated in front of the OCULUS Keratograph® 5M (K5M) with their chin on the chin rest and head against the forehead rest. The investigator will select the Tear Meniscus Height feature from the TF-Scan section on the K5M. The infrared (IR) illumination setting will be used. The camera will be adjusted so the tear meniscus is in the centre of the image. The device will project rings of light (Placido discs) onto the tear film. The participant will be instructed to look straight ahead and an image of each eye will be taken. TMH will be calculated as the average of two measures taken using the on-screen calipers.

#### 4.5.6 OBJECTIVE NON-INVASIVE KERATOGRAPH® BREAK UP TIME (NIK BUT)

---

The participant will be seated in front of the OCULUS Keratograph® 5M with their chin on the chin rest and head against the forehead rest. The investigator will select the NIK BUT feature from the TF-Scan section on the K5M. The participant will be instructed to blink twice and then keep looking straight ahead while keeping their eyes open for as long as they can. The K5M software will automatically display the time passed from the second blink until the first distortion of the rings. Three measurements will be taken from each eye and the median value will be used for each eye.

#### 4.5.7 LIPID LAYER THICKNESS (EASYTEAR®VIEW+)

---

The participant will be seated at a slit lamp and a diffuse white light will be shone onto the participant's eye. Lipid layer thickness will be graded according to the interference pattern observed based on Guillon and Guillon's classification system^7 (open meshwork, closed meshwork, wave, amorphous, colour fringe, and other).

#### 4.5.8 MEIBOMIAN GLAND ASSESSMENT

---

Participants will be seated at a slit lamp biomicroscope with the magnification set to 10x or 16x. The participant will be asked to look up and away from their nose. The meibomian glands will be manually expressed using the MG Evaluator (TearScience/J&J). The MG Evaluator will be depressed halfway to apply a pressure of 1.2 g/mm^2 to the centre of the lower eyelid just below the lash line and angled down approximately 15 to 45 degrees. The MG Evaluator will be depressed halfway to apply a pressure of 1.2 g/mm^2 to three separate areas (nasal, central, temporal) on the lower eyelid just below the lash line and angled down approximately 15 to 45 degrees. Five consecutive glands in each area will be assessed for quality and quantity of expression. Quality of expression will be graded as follows using a modified scale based on Bron and Snibson: 0: clear fluid, 1: cloudy fluid, 2: cloudy particulate fluid, 3: inspissated, like toothpaste and 4: waxy, inexpressible. The results for each eye will be summed. The number of meibomian glands yielding lipid secretion will be graded as follows for each eye: 0: >75% (almost all), 1: 50 – 75% (more than half), 2: 25 – 50% (less than half), 3: <25% (only a few), and 4: ~0% (close to none).

